4.2.2 Intensity of adverse events

The intensity of clinical AEs is graded on a three-point scale - mild, moderate, severe - and is reported on specific AE form of the eCRF.

If the intensity of an AE worsens during study drug administration, only the worst intensity must be reported on the AE form. If the AE lessens in intensity, no change in the intensity is required.

The three categories of intensity are defined as follows:

□ Mild

The event may be noticeable to the patient. It does not influence daily activities and usually does not require intervention.

D Moderate

The event may make the patient uncomfortable; performance of daily activities may be influenced; intervention may be needed.

□ Severe

The event may cause noticeable discomfort and usually interferes with daily activities. The patient may not be able to continue in the study, and treatment or intervention is usually needed.

A mild, moderate or severe AE may or may not be serious [see Section 4.3.1]. These terms are used to describe the intensity of a specific event (as in mild, moderate, or severe myocardial infarction). However, a severe event (such as severe headache) may be of relatively minor medical significance and is not necessarily serious. For example, nausea lasting several hours may be rated as severe, but may not be clinically serious. Fever of 39 °C that is not considered severe may become serious if it prolongs hospital discharge

Ponesimod / ACT-128800 / JNJ-67896153 Multiple Sclerosis		EudraCT 2009-011470-15 EDMS-ERI-206617631
Protocol AC-058B202	Confidential	
Version 12		
15 March 2022, page 116/179		

by a day [see Section 4.3.1.2]. Seriousness rather than severity serves as a guide for defining regulatory reporting obligations.

These definitions do not apply to clinically significant and asymptomatic laboratory test abnormalities or abnormal assessments (e.g., ECG findings) considered as AEs. The investigator must select "non-applicable" on the AE form of the eCRF to qualify the intensity of the AE.

4.2.3 Relationship to study drug

Each AE must be assessed by the investigator as to whether or not there is a reasonable possibility of causal relationship to the study drug and reported as either related or unrelated.

Related to study drug

This category applies to any AE (whether serious or not) that appears to have a reasonable possibility of causal relationship to the use of the study drug (i.e., a relationship cannot be ruled out). Guidelines to determine whether an event might be considered related include (but are not limited to) the following:

- The event occurred in close temporal relationship to study drug administration.
- The event abated (diminished) or disappeared when treatment with the study drug was down-titrated, interrupted, or discontinued.
- The event reoccurred when treatment was reintroduced.
- Environmental factors such as clinical state and other treatments could equally have caused the event.

Unrelated to study drug

This category applies to any AE (whether serious or not) that does not appear to have a reasonable relationship to the use of study drug (see above guidelines).

4.2.4 Reporting of adverse events

4.2.4.1 Treatment period (including transition period and study drug interruption)

The end date and outcome of all AEs that occurred during the core study and that are still ongoing when the patient is entering the transition period must be recorded on a separate page of the extension study CRF. In the event that the AE is worsening or becoming serious, it must be recorded as a new AE on the specific AE form of the extension study CRF. The sponsor may contact the investigator to obtain further information.

All AEs that occur from the start of the transition period of the extension study until 15 days after study drug discontinuation must be recorded on specific AE form of the extension study eCRF.

Ponesimod / ACT-128800 / JNJ-67896153 Multiple Sclerosis		EudraCT 2009-011470-15 EDMS-ERI-206617631
Protocol AC-058B202	Confidential	
Version 12		
15 March 2022, page 117/179		

Treatment-emergent AEs are defined as all AEs with onset date from the date of first study drug intake (date of Visit E1 for patients who received placebo in the core study, date of core study Visit 1 for patients who received active treatment in the core study) until 15 days after study drug discontinuation. This definition applies regardless of whether the patient receives commercially available ponesimod after completing study drug treatment.

All AEs occurring during TP1, TP2, and TP3 must be reported on an AE form of the eCRF, regardless of causal relationship. This applies also to AEs occurring during the study drug interruption (e.g., due to planned pregnancy), i.e., all AEs during study drug interruption must be reported on an AE form in the eCRF.

4.2.4.2 Follow-up period

All AEs regardless of causal relationship occurring from 16 days after study drug discontinuation until 30 or 90 days (as applicable) after study drug discontinuation must be recorded on specific AE form of the extension study eCRF.

4.2.5 Follow-up of adverse events

AEs still ongoing after study drug discontinuation for a given patient must be followed up to 30 or 90 days (as applicable) after study drug discontinuation, or until resolution, stabilization or until the event is no longer clinically relevant or until the event is otherwise explained.

4.3 Serious adverse events

4.3.1 Definitions

4.3.1.1 Serious adverse events

An SAE is defined by the International Council for Harmonisation (ICH) guidelines as any AE fulfilling at least one of the following criteria:

- Fatal
- Life-threatening
- Requiring hospitalization as an inpatient or prolongation of existing hospitalization
- Resulting in persistent or significant disability or incapacity
- Congenital anomaly or birth defect
- Is a suspected transmission of any infectious agent via a medicinal product
- Medically significant, or requires intervention to prevent at least one of the outcomes listed above

Life-threatening refers to an event in which the patient was at risk of death at the time of the event. It does not refer to an event that hypothetically might have caused death had it been more severe.

Ponesimod / ACT-128800 / JNJ-67896153 Multiple Sclerosis		EudraCT 2009-011470-15 EDMS-ERI-206617631
Protocol AC-058B202	Confidential	
Version 12		
15 March 2022, page 118/179		

Important medical events that may not immediately result in death, be life-threatening, or require hospitalization may be considered to be SAEs when, based upon appropriate medical judgment, they may jeopardize the patient, and may require medical or surgical intervention to prevent one of the outcomes listed in the definitions above.

The reference safety document to assess whether or not an SAE must be reported by the sponsor to health authorities, ECs/IRBs and investigators in an expedited fashion is the Investigator's Brochure [Ponesimod IB].

4.3.1.2 Hospitalization - Prolongation of existing hospitalization

Hospitalization is defined as an admission to a hospital or a prolongation of existing hospitalization due to an AE.

If on Days 1, 8, or 15 a patient needs to stay at the hospital more than 12 hours post-dose due to an AE, this constitutes an SAE.

The following reasons for hospitalizations are not considered AEs, and therefore not SAEs:

- Hospitalizations for cosmetic elective surgery, social and/or convenience reasons.
- Standard monitoring of a pre-existing disease or medical condition that did not worsen, e.g., hospitalization for coronary angiography in a patient with stable angina pectoris.
- Elective treatment of a pre-existing disease or medical condition that did not worsen, e.g., elective hip replacement for arthritis. Complications that occur during hospitalization are AEs or SAEs (for example if a complication prolongs hospitalization).

4.3.1.3 Serious adverse events related to study-mandated procedures

Such SAEs are defined as SAEs that appear to have a reasonable possibility of causal relationship (i.e., a relationship cannot be ruled out) to study-mandated procedures (excluding administration of study drug) such as complication of a mandated invasive procedure (e.g., blood sampling, heart catheterization), or car accident on the way to the hospital for a study visit, etc.

4.3.2 Reporting of serious adverse events

4.3.2.1 Treatment period (including transition period and study drug interruption)

All SAEs regardless of causal relationship that occur from the start of the transition period until 15 days after study drug discontinuation must be recorded.

Treatment-emergent SAEs are defined as all SAEs with onset date from the date of first study drug intake (date of Visit E1 for patients who received placebo in the core study, date of core study Visit 1 for patients who received active treatment in the core study) until 15 days after study drug discontinuation.

Ponesimod / ACT-128800 / JNJ-67896153 Multiple Sclerosis		EudraCT 2009-011470-15 EDMS-ERI-206617631
Protocol AC-058B202	Confidential	
Version 12		
15 March 2022, page 119/179		

These SAEs are reported on SAE forms and also on the AE form in the extension study eCRF. Therefore, they are entered both in the drug safety and clinical databases, and must be reconciled before study closure.

All SAEs occurring during TP1, TP2, and TP3 must be reported on an AE page of the CRF, regardless of causal relationship. This applies also to SAEs occurring during study drug interruption (e.g., due to planned pregnancy), i.e., all SAEs during study drug interruption must be reported on SAE forms and also on the AE form of the eCRF.

4.3.2.2 Follow-up period

All SAEs regardless of causal relationship occurring from 16 days after study drug discontinuation until 30 or 90 days (as applicable) after study drug discontinuation must be reported.

These SAEs are reported on SAE forms and also on the AE form in the eCRF. Therefore, they are entered both in the drug safety and clinical databases, and must be reconciled before study closure.

4.3.2.3 Reporting procedures

All SAEs, as well as product quality complaints (PQCs), occurring during the study must be reported to the appropriate sponsor contact person by study site personnel within 24 hours of their knowledge of the event.

All SAEs must be recorded on SAE forms, irrespective of the study drug received by the patient, whether or not this event is considered by the investigator to be related to study drug.

These SAE forms must be completed and signed by a physician from the study site and sent to the sponsor within 24 hours using the contact details provided on the form. The investigator must complete the SAE form in English (unless otherwise specified) and assess the relationship to study drug.

Such preliminary reports will be followed by detailed descriptions that should include copies of hospital case reports, autopsy reports, hospital discharge summaries and other documents when requested and applicable. Follow-up information about a previously reported SAE must also be reported within 24 hours of receiving it. The sponsor may contact the investigator to obtain further information.

Suspected (considered related to the study drug) and unexpected (not previously described in the reference safety document) serious adverse reactions (SUSARs) will be expedited by the sponsor to health authorities, ECs/IRBs and investigators, as appropriate. Unblinding of SUSARs will be performed as appropriate.

Ponesimod / ACT-128800 / JNJ-67896153 Multiple Sclerosis		EudraCT 2009-011470-15 EDMS-ERI-206617631
Protocol AC-058B202	Confidential	
Version 12		
15 March 2022, page 120/179		

MS relapses and associated symptoms are exempt from being reported on an SAE form by the investigator to the sponsor, with the following exceptions:

- MS relapses with fatal outcome.
- MS relapses that, in the view of the investigator, warrant specific notice due to unusual frequency, severity or remarkable clinical manifestations (these should be reported as an AE on the AE form of the eCRF and, if applicable, on the SAE form).

4.3.3 Follow-up of serious adverse events

SAEs still ongoing at the EOS2 or EOS3 must be followed until resolution or stabilization or until the event is otherwise explained.

New SAEs occurring at any time after the EOS / after the 30-day follow-up period may be reported to the sponsor within 24 hours of the investigator's knowledge of the event, if felt appropriate by the investigator. Therefore, these SAEs are entered only into the drug safety database and hence will not affect study closure.

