4 SAFETY DEFINITIONS AND REPORTING REQUIREMENTS

4.1 Summary table

Periods	Treatment (including transition and study drug interruption)	Follow-up ²	After Follow-up
Time frame	During study drug administration until 15 days after study drug discontinuation and during study drug interruption	Treatment period 1: From 16 until 30 days after study drug discontinuation Treatment periods 2 and 3: From 16 until 90 days after study drug discontinuation	Treatment period 1: After 30 days Treatment periods 2 and 3: After 90 days
AE/SAE reporting on eCRF AE form	All AEs/SAEs	All AEs/SAEs	None
SAE reporting on SAE form	All SAEs	All SAEs	If felt appropriate by investigator
Reconciliation ¹	Yes	Yes	Not applicable

1. Reconciliation between clinical and drug safety databases.

2. AEs/SAEs occurring between treatment periods 1, 2 and 3 must be reported in the AE eCRF form.

AE adverse event; eCRF electronic case report form; SAE serious adverse event.

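### Protocol 4.3.3 gives TP2/TP3 patients two different dates, day 30 and day 90, from which reporting of new SAEs becomes optional

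*Protocol*

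**What the plan says.** Protocol 4.3.3 (Follow-up of serious adverse events) states that "New SAEs occurring at any time after the EOS / after the 30-day follow-up period may be reported to the sponsor" where the investigator thinks it appropriate. It then draws the database consequence: "these SAEs are entered only into the drug safety database and hence will not affect study closure". Nothing restricts the 30 days to TP1, although the sentence just before it, on SAEs still ongoing, names both EOS2 and EOS3.

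The reporting rules proper differ by treatment period:

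- Protocol 4.3.2.2 (Follow-up period) covers SAEs "occurring from 16 days after study drug discontinuation until 30 or 90 days (as applicable) after study drug discontinuation must be reported". Of these events it says that "they are entered both in the drug safety and clinical databases, and must be reconciled before study closure".
- The summary table in Protocol 4.1 gives the follow-up period as "Treatment periods 2 and 3: From 16 until 90 days after study drug discontinuation", with all SAEs on both the SAE form and the eCRF AE form, and with reconciliation. Its discretionary period begins later: "Treatment periods 2 and 3: After 90 days".
- Protocol 3.1.1 puts EOS2 at 30 days after the last dose for TP1 and EOS3 at 90 days for patients who entered TP2 or TP3.

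**The concern.** For a TP2/TP3 patient, end of study and the end of a 30-day follow-up are different dates, yet 4.3.3 joins them with a slash as if they were one. A site that takes the 30-day half literally would treat an SAE on, say, day 45 as optional and as belonging only in the drug safety database. Sections 4.1 and 4.3.2.2 make the same event mandatory in both databases.

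Two errors could follow: the event is not reported, or it is reported but never reaches the clinical database from which the tables are built. The outputs exposed are:

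- the protocol's post-treatment SAE endpoint, which runs to day 90 (Protocol 3.10.2, with tabulation or listing in 5.6);
- the SAP's post-treatment-emergent AE tables (SAP 5.4.4.3.3), whose window ends at the last study date (SAP 5.1.6 and 5.4.3.2);
- the SAP's table of all SAEs by system organ class and preferred term, and its SAE listings (SAP 5.4.4.4.2).

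Long-term safety is one of the study's stated objectives, so the completeness of these outputs matters.

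**Working it through.** **Which follow-up length the protocol is built on.** Protocol 3.1.1 gives a maximum study duration of 649 weeks per patient, made up of 636 weeks of treatment plus follow-up.

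- With 90 days: 636 + 90/7 = 636 + 12.86 = 648.86, which rounds to 649. This reproduces the stated figure.
- With 30 days: 636 + 30/7 = 636 + 4.29 = 640.29. This does not.

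The protocol's own total therefore uses 90 days for patients who go through TP2/TP3.

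**The rules side by side for a new SAE in a TP2/TP3 patient.**

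| Days after last dose | 4.1 and 4.3.2.2 | 4.3.3 read through EOS (day 90) | 4.3.3 read through 30 days |
|---|---|---|---|
| 16 to 30 | Mandatory, both databases | Not yet optional | Not yet optional |
| 31 to 90 | Mandatory, both databases | Not yet optional | Optional, safety database only |
| After 90 | Optional | Optional, safety database only | Optional, safety database only |

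The conflict is confined to the middle row and to the last column. For patients who stop in TP1, EOS2 is day 30, so both readings of 4.3.3 coincide and there is no conflict.

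**Length of the disputed window.**

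- TP2/TP3 follow-up reporting window: 90 − 16 + 1 = 75 days.
- Disputed part: 90 − 31 + 1 = 60 days.
- Share: 60/75 = 80% of the calendar window.

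If 4.3.3 is aligned with 4.1 and 4.3.2.2, the disputed window falls from 60 days to 0.

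**What the arithmetic does not give.** The 80% is a share of days. The documents contain no count or rate of SAEs after day 30, so the number of events at risk cannot be computed. No sample size, power or error-rate figure depends on this point.

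**The case against.** The strongest reply is that 4.3.3 can be read consistently. It mentions end of study first, and for TP2/TP3 that is day 90. On that reading it agrees with 4.1, which states the same discretionary rule and starts it after 90 days. This stands as a possible reading, but the sentence offers the 30-day alternative without restriction and gives no rule for choosing between the two.

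The second reply is that the duty to day 90 does not hang on 4.3.3. It is explicit in 4.1 and 4.3.2.2. Protocol 4.2.4.2 separately requires all AEs to 30 or 90 days, as applicable, on the eCRF, and an SAE is an AE. Protocol 4.3.2.3 requires SAEs that occur during the study to be reported within 24 hours. AEs and SAEs are also recorded at the day-90 visit, FU3 (Protocol 3.12.4.5), including for patients who have switched to commercial ponesimod (3.12.4). All of this stands, and it limits the consequence to a risk.

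A reader might go further and infer that the protocol makes late SAEs optional for TP2/TP3 patients, so that most post-treatment SAEs will be lost. The documents do not support that: the mandatory rule is stated several times, and 80% describes days and not events. Nor should a reader infer that a dedicated SAP summary of post-treatment-emergent SAEs would be incomplete. None is planned: SAP 5.4.4.3.3 covers AEs as a whole, and SAP 5.4.4.4.2 covers treatment-emergent SAEs and all SAEs.

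The last reply is timing. The protocol plans the last patient's last visit for Q4 2023, and the SAP was approved on 20 September 2023. New wording can affect little of the remaining follow-up. That is fair, and it makes a check of the data more useful than the wording change alone.

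**Conclusion.** The point holds as an internal inconsistency. The unqualified 30-day cut-off in 4.3.3 is wrong for TP2/TP3 and conflicts with 4.1 and 4.3.2.2 over days 31 to 90, which is 60 days. It does not affect patients followed up under TP1 only.

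The effect on the data is a possibility and not a stated outcome: some SAEs in that window may be unreported, or may sit only in the drug safety database. This assumes that at least some sites applied the 30-day half of the sentence, which the documents neither show nor exclude. The correction is worth making because it costs almost nothing and the exposed outputs concern long-term safety.

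**What to change.** Reconcile 4.3.3 with 4.1 and 4.3.2.2. In place of the slash construction, say that discretionary reporting begins after EOS2 for TP1 or EOS3 for TP2/TP3. This introduces no new rule, since it only points to the windows the protocol already defines. If a further amendment is not practical, a short clarification to sites does the same job.

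Before database lock, list all SAEs in the drug safety database with onset on days 31 to 90 after the last dose in TP2/TP3 patients, and confirm that each has a matching record in the clinical database. The cost is one phrase or one site letter, plus a targeted extension of the reconciliation that 4.3.2.2 already requires. This check finds events that were reported but left out of the clinical database. It cannot find events that were never reported, so the site clarification should also ask sites to confirm that none were withheld on the 30-day reading.

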4.4 Pregnancy

In embryo-fetal studies in rats and rabbits ponesimod shows teratogenic potential. Therefore, appropriate precautions must be taken by WOCBP. Women must not become pregnant while on the study drug and until 30 days after study drug discontinuation.

If a woman becomes pregnant when on study drug, study drug MUST be discontinued immediately. The investigator must counsel the patient and discuss the risks of continuing with the pregnancy, and the possible effects on the fetus.

Women who wish to interrupt the study treatment because of planned pregnancy and restart the study treatment after delivery and lactation, if applicable, will be allowed to stay in the study provided the conditions mentioned in the Appendix 1, section D, are fulfilled.

4.4.1 Definition of childbearing potential

The assessment of a woman's childbearing potential can be done at any time during the study. A woman is considered to be of childbearing potential unless she meets at least one of the following criteria:

- Previous bilateral salpingo-oophorectomy or hysterectomy.
- Premature ovarian failure confirmed by a gynecologist.
- Postmenopausal, defined as 12 consecutive months with no menses without an alternative medical cause.

Ponesimod / ACT-128800 / JNJ-67896153		EudraCT 2009-011470-15
Multiple Sclerosis		EDMS-ERI-206617631
Protocol AC-058B202	Confidential	
Version 12		
15 March 2022, page 121/179		

4.4.2 Acceptable methods of contraception

The investigator must explain and stress the importance of using acceptable methods of contraception during the study, and for at least 30 days after study drug discontinuation.

During TP1 and TP2, WOCBP must follow the below contraception scheme:

- Two methods of contraception (one from Group 1 and one from Group 2 below) during the study, and for at least 30 days after study drug discontinuation, as follows:
 - Group 1: Oral, implantable, transdermal or injectable hormonal contraceptives, intrauterine devices, female sterilization (tubal ligation), or partner's sterilization (vasectomy).
 - Group 2: Condoms, diaphragm or cervical cap.

Abstention and rhythm methods were not acceptable methods of contraception during TP1 and TP2.

During TP3, WOCBP must follow the below contraception scheme:

- Two methods of contraception, one must be from Group 1 and one must be from Group 2, defined as follows:
 - Group 1: Oral, implantable, transdermal or injectable hormonal contraceptives, intrauterine devices.
 - Group 2: Condoms, diaphragm or cervical cap.
- Female sterilization (tubal ligation).
- Sterilization of the male partner (vasectomy).
- True abstinence from intercourse with a male partner only when this is in line with the preferred lifestyle of the patient.

Rhythm methods or the use of a condom by a male partner alone are not considered acceptable methods of contraception.

If during the study a switch to a hormonal contraceptive from Group 1 is considered, it must be taken for at least 1 month in parallel to previous forms of contraception from Group 1, and contraception from Group 2 must remain in use throughout the study period.

If there is any doubt on what contraceptive advice should be given to an individual patient, consultation with a gynecologist is recommended.

CONFIDENTIAL - FOIA Exemptions Apply in U.S.

Ponesimod / ACT-128800 / JNJ-67896153 Multiple Sclerosis		EudraCT 2009-011470-15 EDMS-ERI-206617631
Protocol AC-058B202	Confidential	
Version 12		
15 March 2022 nage 122/179		

